Once they are enrolled, pilot subjects will be screened during a face-to-face interview with a member of the study staff. Pilot participants will be screened to ensure that they are not color-blind, claustrophobic, or have metal in their body. Female pilot subjects who are pregnant, planning on becoming pregnant, or who cannot confirm they are not pregnant will not be eligible. Pregnancy status will be obtained at two levels of our experimental procedures. First, we will ask that they read and sign a statement at the end of the consent document confirming that they are not pregnant. Second, our MRI technicians will ask all female subjects to confirm that they are not pregnant prior to entering the scanner for each scan.

Subjects:

Sixty-eight U.S. military veterans of the Gulf War (1990-1992) with chronic musculoskeletal pain (**ages 35-65 yrs**) will be recruited and randomly assigned in blocks (to ensure 34 participants in each group) using the Research Randomizer tool (randomizer.org) to 16 weeks of RET or WLC.

Screening and exclusion criteria:

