
Study Schedule

This study will take approximately 6 years to complete. Due to unanticipated delays we did not make our originally projected start date of (January 1, 2011). Thus study procedures, including recruiting and the review of patient records for that purpose, were not initiated until January, 2013. We plan on testing 6 cohorts under each condition and individual cohorts will be involved in the study for 16 months. We anticipate completing the last training session in approximately 3.5 years and concluding the last follow-up in approximately 4.5 years.

Subjects will be recruited by direct contact, letter, peer referral, or advertisement and will be screened over the phone prior to written consent and the first day of testing. A confirmation letter and packet that contains introductory study information will be mailed to individuals who meet eligibility criteria based on the phone screener. Informational packet will include a copy of the consent form, a description of fMRI, and a map and driving directions to the Madison VA. Individuals who are eligible will also be invited to attend an informational session at the VA hospital. Attendance at the session is not mandatory for participation. The informational session is designed to provide potential subjects with information regarding study participation and reduce subject attrition following enrollment. During this session project staff will cover: 1) study design, 2) time commitment for participation, 3) time-line for participation, 4) description of the RET training program, 5) subject responsibilities (i.e. attend sessions as scheduled) and 6) subject compensation as detailed in the consent form. Subjects will have an opportunity to read through the consent form (signing of consent form will not occur at this time) and ask any questions they might have. Subjects will also have the opportunity to schedule their baseline testing session. Scheduling can also be completed over the phone at a later date. Potential subjects who attend the informational session and are not interested in participating will not be contacted further regarding this study.

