Following enrollment, subjects will be asked to undergo five phases of testing that will include: 1) a clinical interview and a clinical assessment at the Madison VA hospital; 2) psychophysical and cognitive testing in a mock MRI environment; 3) repeated psychophysical, cognitive, and physical activity assessments as well as functional neuroimaging, which will overlap with; 4) a 16-week resistance training exercise (RET) regimen or wait-list control (WLC) depending on group assignment; and 5) follow-up with test sessions at 6 and 12 months after the completion of primary testing. The clinical interview will occur following written consent and will be completed on the first day of testing in a private office at the VA hospital. A clinical assessment will also occur in a private exam room at the Madison VA following written consent to ensure study eligibility. Upon completion of the clinical interview and assessment, testing will commence and will consist of filling out questionnaires, participating in psychophysical and cognitive performance testing and undergoing MRI environment habituation in a mock MRI. After completing the initial test day and confirming the Veteran's eligibility to continue participation they will be assigned to their condition, either RET or WLC, and scheduled for the baseline MRI scan. We plan to test in cohorts of 12 Veterans, 6 in each condition, by screening individuals over a 1-2 month period and conducting baseline scans for all cohort members over a 2-week period. The RET regimen and WLC will begin the week following the baseline scan and continue for 16-weeks. Veterans in both conditions will make 3 lab visits during the course of the RET/WLC with a fourth lab visit after the 16-week intervention has concluded. Two follow-up lab visits will take place at 6 and 12 months after the completion of the primary testing. A bulleted version of the study schedule appears below:

◆ Pilot testing

- We plan to enroll enough pilot subjects to test the exercise and brain scanning procedures on 5 individuals. Pilot subjects will be asked to complete a modified version of the brain scanning procedures which will include the administration of painful stimuli, cognitive task and perceptual rating.

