Power estimates for the trial are based on Specific Aim 1. General multivariate regression models will be used to estimate the time averaged difference in pain ratings and clinical symptom scores (continuous measurements) between the treatment and the control group. With general multivariate regression models we model both the dependence of the response on the explanatory variables as well as the autocorrelation among the responses. In order to achieve 90% power, at alpha equal to .05, with an effect size of .6 (minimum effect size of clinical importance) and with a correlation of .6 between measurements from each individual, the necessary sample size would be 34 subjects per group. If we take into account a 20% subject attrition rate, then the total sample size should be 41 subjects per group. All randomized subjects will be included in the analysis within the appropriate arm that they were randomly assigned (i.e. an intent-to-treat analysis will be used). Noncompliance, protocol deviations, withdrawal or any other problem that occur after randomization will be ignored and the participant's last observed data points will be carried forward in the analyses. Missing data will be assumed to be missing completely at random and appropriate missing data methods will be used (i.e. multiple imputation) to minimize the effect of withdrawal. For the purpose of evaluating Specific Aim 2, a similar methodology will be employed to estimate the time averaged difference in physical activity counts as measured by accelerometry.

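### The trial randomises 34 per group, the figure before attrition, although its own calculation asks for 41 per group after 20% loss; the 90% power is not supported as written

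*Combined protocol and SAP*

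**What the plan says.** The Statistical Considerations section bases power on Specific Aim 1 and on a time-averaged difference between the groups. It reads "In order to achieve 90% power, at alpha equal to .05, with an effect size of .6", adds a correlation of 0.6 between measurements on the same person, and concludes that "the necessary sample size would be 34 subjects per group". The next sentence adds attrition: "If we take into account a 20% subject attrition rate, then the total sample size should be 41 subjects per group".

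The Subjects section sets the enrolment. It names "Sixty-eight U.S. military veterans of the Gulf War (1990-1992) with chronic musculoskeletal pain" as those to be recruited and randomised in blocks, "to ensure 34 participants in each group".

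The Study Schedule adds "We plan on testing 6 cohorts under each condition" and "We plan to test in cohorts of 12 Veterans, 6 in each condition".

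The power paragraph does not say whether the test is one- or two-sided, how many measurements enter the average, what form the correlation takes, or how the baseline value is used. For missing data it names both carrying the last observation forward and multiple imputation, within an intent-to-treat analysis.

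**The concern.** The Subjects section describes people recruited and randomised, not people who finish. Its 34 per group is therefore the number before attrition, and the documents do not explain why the allowance was dropped. The power paragraph also omits the inputs needed to reproduce 34.

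The power statement covers the trial's main efficacy question. A null result on pain or physical function would be read against a stated 90% chance of detecting an effect of 0.6, described as the smallest of clinical importance. If the randomised sample delivers less, that reading is too confident.

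**Working it through.** **Inputs.** From Statistical Considerations: d = 0.6, correlation 0.6, alpha 0.05, power 90%, 34 per group, 20% attrition, 41 per group. From Subjects: 68 randomised, 34 per group. The number of measurements m is my assumption:

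- m = 4 for baseline and weeks 6, 11 and 17.
- m = 3 without baseline.
- m = 6 with the 6- and 12-month visits added.
- m = 16 to 18 if the weekly symptom questionnaires are used.

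**Step 1: enrolment against requirement.** 2 x 41 = 82 required; 2 x 34 = 68 randomised. The shortfall is 14 subjects, 7 per group. No assumption is involved.

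**Step 2: the inflation.** 34 x 1.2 = 40.8, rounded up to 41, which is the plan's figure. But 41 x 0.8 = 32.8, about 33, which is below 34. The correct form is 34/(1 - 0.20) = 42.5, so 43 per group.

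**Step 3: the 34 taken at face value.** If 34 gives exactly 90% two-sided, the standardised effect is 1.960 + 1.282 = 3.242. Losing 20% multiplies it by sqrt(0.8), giving 2.899. Power is then Phi(2.899 - 1.960) = 0.83. One-sided, 2.926 x sqrt(0.8) = 2.617 and Phi(2.617 - 1.645) = 0.83. This treats dropouts as contributing nothing.

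**Step 4: reproducing 34 under constant correlation, no baseline adjustment.**

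n per group = 2(z_a + z_b)^2 v / d^2, with v = [1 + (m-1) x 0.6]/m.

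Power = Phi(d / sqrt(2v/n) - z_a).

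The 27 in the table is 34 x 0.8 = 27.2, rounded down.

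| m | v | n, two-sided | Power, 34 per group | Power, 27 per group |
|---|---|---|---|---|
| 3 | 0.733 | 42.8 | 0.82 | 0.73 |
| 4 | 0.700 | 40.9 | 0.84 | 0.75 |
| 5 | 0.680 | 39.7 | 0.85 | 0.76 |
| 6 | 0.667 | 38.9 | 0.86 | 0.77 |
| 18 | 0.622 | 36.3 | 0.88 | 0.80 |
| limit | 0.600 | 35.0 | 0.89 | 0.81 |

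Under these assumptions 34 per group stays below 90% two-sided for any number of measurements. A one-sided 0.05 test with m = 4 needs 33.3, which rounds up to 34 and matches the plan.

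**Step 5: other routes to about 34, two-sided.**

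- Decaying AR(1) correlation of 0.6 between adjacent visits, m = 4, simple mean: v = [4 + 2(3 x 0.6 + 2 x 0.36 + 0.216)]/16 = 0.592, so n = 34.6 and power at 34 is 0.895.
- The same with generalised least squares: v = 1.6/(4 - 2 x 0.6) = 0.571, so n = 33.4, which rounds up to 34.
- Constant correlation, three post-baseline visits, change from baseline: v = 0.733 + 1 - 1.2 = 0.533, so n = 31.1, i.e. 32. Power is 0.92 with 34 per group and 0.855 with 27.
- The same with baseline as covariate (ANCOVA): v = 0.733 - 0.36 = 0.373, so n = 21.8, i.e. 22. Power is 0.98 with 34 per group and 0.95 with 27.

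**The case against.** The strongest reply is that Step 4 fixes things the plan leaves open. The plan speaks of autocorrelation among responses. An AR(1) reading brings a two-sided test with four measurements to 34 or 35 per group, so a reader who infers from the m = 4 match that 34 holds only for a one-sided test goes further than the documents allow. With sidedness, m and correlation structure all free, one match does not identify what was done. This objection stands: one-sidedness is possible but not shown.

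A reader might also infer that 68 subjects cannot have 90% power. That does not follow either. The Summary of Experimental Design says the primary aims compare baseline with end of treatment. On the plan's own d and correlation, a change-score or ANCOVA analysis of three post-baseline visits exceeds 90% with 34 per group, and ANCOVA does so even with 27. However, the power paragraph does not specify baseline adjustment, and neither figure reproduces 34.

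The 27-per-group figures assume dropouts contribute nothing, while the plan keeps every randomised subject through carry-forward or imputation. Taking the effect of 0.6 as unaffected by how gaps are filled, those figures are a lower bound. Still, the plan itself treats 20% attrition as requiring a larger sample.

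Finally, six cohorts of 12 make 72, which might look like a third enrolment target. It is a schedule: 68/12 = 5.67, so six cohorts hold 68 with the last partly filled.

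None of this touches Steps 1 and 2.

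**Conclusion.** Two things hold without assumption. The plan randomises 68 where its own calculation calls for 82, and its inflation gives 41 per group where 43 is correct. The second error is small, at two per group.

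The size of the power loss is conditional. For a time-averaged difference with constant correlation 0.6, no baseline adjustment and a two-sided 0.05 test, 34 per group gives 82-86% for 3 to 6 measurements and about 88% with weekly scores. With 20% contributing nothing, the figures are 73-77% and about 80%, as a lower bound. Using weekly scores assumes that the primary measures are in the weekly battery, which the plan does not say.

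The documents do not establish that the test is one-sided, nor that 90% is out of reach under every analysis. They establish that the stated 90% lacks the plan's own attrition allowance and cannot be verified from what is written.

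**What to change.** In Statistical Considerations, state the sidedness (two-sided unless justified), the number of measurements, the correlation structure and the baseline handling behind the calculation. On those assumptions, give the power that 68 randomised subjects deliver without attrition and with 20% attrition, in place of 90%. Correct the inflation to n/(1 - 0.20).

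Make the sample size in the Subjects section and in Statistical Considerations agree, and word the cohort plan in the Study Schedule so that it is consistent with that number.

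This needs no added enrolment, only protocol wording. The downside is that the stated power becomes less favourable.

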There are no known efficacious treatments for sick GV's who were deployed to the Persian Gulf. In the absence of a clear etiology (e.g. chemical exposure, physical trauma), studies aimed at addressing symptoms and improving the quality of life of our Veterans are needed.

One consistently efficacious treatment for chronic musculoskeletal pain is exercise (20-22). Exercise training has been shown to result in improved physical function, decreased symptoms, increased feelings of energy and decreased feelings of depressed and anxious mood for a host of chronic pain conditions including peripheral arterial disease, widespread pain and fatigue, rheumatoid arthritis and fibromyalgia (21, 22). The most relevant comparison group for GV's with CMP is FM, a disorder with a primary symptom of widespread and medically unexplained muscle and joint pain, occurring predominantly in civilian women (23). In FM, a recent meta-analysis of aerobic exercise training found beneficial effects for physical function ($d = 0.66$ standard deviations), global well-being ($d = 0.49$), and pain ($d = 0.65$) (20). Only 3 RET interventions met criteria for inclusion in the review. Although the RET trials were rated as possessing low methodological quality, the results were promising showing large positive effects for global well-being ($d = 1.43$), depression ($d = 1.14$) and pain ($d = 1.68$) and a moderate positive effect on physical function ($d = 0.52$). Of the 1264 subjects assigned to exercise training, only five adverse events possibly related to exercise were reported and none were reported for strength training. One study noted that "...after the initial phase of training, the patients did not complain of any unusual exercise-induced pain or muscular soreness during the experimental period, and even intensive strength training did not worsen the symptoms". In contrast, exacerbation of symptoms was thought to have a negative impact on adherence, but was poorly tracked and reported. The authors concluded that aerobic exercise training produces important benefits for FM patients and that limited evidence suggests that strength training may have a greater effect on the patients' primary complaints of muscle pain. A recent

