We are aware of only one exercise training trial in GVs. Donta et al. (16) conducted a large scale treatment trial of aerobic exercise training and cognitive behavioral therapy (CBT) in GVs with chronic multisymptom illnesses including persistent pain, fatigue and cognitive complaints. For VA Cooperative Study #470, 1092 Veterans were randomly assigned to Exercise (n=269), CBT (n=286), Exercise plus CBT (n=266) or usual care (n=271). Exercise training consisted of one supervised laboratory session of low intensity exercise aerobic exercise per week for 12 weeks. The exercise prescription was intended to increase physical activity levels. Exercise intensity was determined by the participant and not reported. Veterans were encouraged to exercise an additional two to three times per week during the 12 week treatment trial, but adherence to this suggestion was not reported. For CBT, Veterans met in groups with a licensed therapist once per week for 60-90 minutes. Results indicated modest improvements for both exercise and CBT with respect to physical function (11.7 % and 18.5 %, respectively), but little improvement in pain. Secondary outcome improvements for exercise were found for fatigue, distress, cognitive symptoms and mental health. Adherence to exercise was poor with a median attendance of 6 exercise sessions over the 12 week trial and only 47% considered as treatment adherent. We believe that this trial had several limitations that greatly attenuated the treatment’s effectiveness. The primary limitations were: 1) an exercise prescription requiring only one supervised session, 2) use of a non-standardized exercise prescription not designed for progressive increases in intensity, frequency or duration, 3) failure to measure physical activity when the trial was designed to increase this behavior, and 4) poor adherence to both exercise and CBT conditions. Therefore, we believe that it is premature to discount exercise training as a treatment for GVs with CMP. In fact, it can be reasonably argued that exercise “training” did not occur in this large scale study with only 6 single bouts of exercise being attended. We also agree with the statements made by Hotopf (24) that, “*Despite the importance of large pragmatic trials, additional small trials of focused treatments in specialty settings are required to develop and assess appropriate treatments for GWVI.*”, and that it is useful “...*to establish whether a treatment can work under ideal conditions before attempting to determine whether it does work in the real world.*”

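### The plan applies both last-observation-carried-forward and multiple imputation to withdrawals without ranking them, so the primary estimate is not uniquely defined, and it is biased if carry-forward is followed while the effect builds over time

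*Combined protocol and SAP*

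**What the plan says.** The missing-data rules stand in three consecutive sentences under Statistical Considerations, just after the sample-size text. All randomised participants are analysed in their assigned arm. Events after randomisation, among them withdrawal and poor compliance, are to be disregarded, and for the people affected the rule reads: "last observed data points will be carried forward in the analyses. Missing data will be assumed to be missing completely at random". The plan then turns to imputation and directs it at those same withdrawals, stating that "appropriate missing data methods will be used (i.e. multiple imputation) to minimize the effect of withdrawal".

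The same section plans a general multivariate regression model for the time-averaged difference between arms, with autocorrelation between visits, and allows for 20% attrition. Outcomes are retested at weeks 6, 11 and 17 (Baseline Assessment and 16-Week Trial). The Summary of Experimental Design says that the primary aims compare baseline with the end of treatment. The primary measures are pain scales, the SF-36 physical component summary and the patient global impression of change, PGIC (Day 1 (Screening Day)).

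Three other places bear on why data might be missing. The background section on resistance training reports, from fibromyalgia exercise trials, that "exacerbation of symptoms was thought to have a negative impact on adherence, but was poorly tracked and reported". It also reports that in the earlier aerobic exercise trial in Gulf War Veterans "only 47% considered as treatment adherent". The Safety Monitoring Plan (Interviews and Questionnaires) removes from the study any participant who becomes suicidal.

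**The concern.** The two rules address the same missing values. Once a value has been carried forward, nothing is left to impute. With no stated order, the analyst can choose the method after seeing the data, and the two methods need not agree.

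Carry-forward also suits this design poorly. Training starts with very light loads and progresses, so an early value need not stand for an end-of-treatment value. A filled value is treated as if it had been measured, so the standard error ignores the uncertainty of filling it. PGIC rates change, so a participant who leaves before week 6 has no meaningful baseline value to carry.

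The plan has no sensitivity analysis for dropout related to symptoms. What is at stake is the main efficacy estimate: which number is reported, and how far it lies from the effect the trial was meant to measure.

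**Working it through.** **The plan's own figure.** Inputs from Statistical Considerations: alpha 0.05 (sidedness not stated), power 90%, effect δ = 0.6 SD, correlation ρ = 0.6. The number of measurements m is not stated; baseline plus weeks 6, 11 and 17 gives m = 4.

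n per group = 2(z_α + z_0.90)² × [1 + (m − 1)ρ]/m ÷ δ²

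- One-sided: 2 × (1.645 + 1.282)² × 0.70 ÷ 0.36 = 33.3, so 34, as stated.
- Two-sided: 2 × (1.960 + 1.282)² × 0.70 ÷ 0.36 = 40.9, so 41.
- Attrition: 34 × 1.2 = 40.8, so 41, as stated.

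The missing-data rule enters none of these, so the sample-size text does not show which rule was intended.

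**Can the two rules be reconciled?** One might read carry-forward as the rule for withdrawals and imputation as the rule for isolated missed visits. The text rules this out, because it ties imputation to withdrawal by name. Nothing elsewhere ranks the two, calls one a sensitivity analysis, or describes an imputation model.

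**What carry-forward does when dropout is completely at random.** Assumptions (the documents give only the 20% and the 0.6):

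- effect of 0.2, 0.4 and 0.6 SD at weeks 6, 11 and 17;
- 20% dropout in each arm;
- last visit at baseline, week 6 or week 11, one third each;
- dropouts would have had the same mean effect as the others had they stayed.

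End of treatment: the mean effect carried by dropouts is (0 + 0.2 + 0.4)/3 = 0.2.

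0.8 × 0.6 + 0.2 × 0.2 = **0.52**, against a true 0.60.

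Time-averaged over the three visits: the true value is (0.2 + 0.4 + 0.6)/3 = 0.40. Dropouts contribute:

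- last seen at baseline: 0
- last seen at week 6: (0.2 + 0.2 + 0.2)/3 = 0.2
- last seen at week 11: (0.2 + 0.4 + 0.4)/3 = 0.333

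Their mean is 0.178, and 0.8 × 0.40 + 0.2 × 0.178 = **0.36**.

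A simulation of 1,500 trials (34 per arm, equal correlation 0.6 between visits) gave 0.521 and 0.355. Complete data gave 0.602 and 0.400, and completers alone 0.601 and 0.398. Valid imputation would also be unbiased here, so the two prescribed rules give different answers.

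If the effect is a constant 0.6 from week 6, the carried mean is (0 + 0.6 + 0.6)/3 = 0.4, and the result is 0.8 × 0.6 + 0.2 × 0.4 = 0.56.

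**What carry-forward does when the poorest early responders leave.** Same building effect and simulation set-up, with those whose pain changed least favourably by week 6 leaving after that visit. The true end-of-treatment effect is 0.60.

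| Dropout RET / WLC | Carry-forward, week 17 |
|---|---|
| 20% / 20% | 0.52 |
| 30% / 10% | 0.41 |
| 53% / 10% | 0.29 |
| 10% / 30% | 0.65 |

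The splits are assumptions; 53% is the complement of the 47% adherence in the earlier trial. The error can go in either direction.

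**The case against.** The strongest reply is that much of a sound plan is already present. All randomised participants are kept, a repeated-measures model is specified, and imputation is named. Stating missing-completely-at-random does no harm by itself, since imputation and a likelihood-based repeated-measures model need only missing-at-random. This stands: bias arises only if carry-forward is followed. The lack of an order of priority does not depend on that.

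A reader might infer that the background contradicts the missing-completely-at-random assumption. It does not go that far. The remark on symptom flares is hedged, concerns fibromyalgia trials, and is about adherence rather than missing outcomes. A non-adherent participant can still be measured. With the 47% adherence and the removal rule, it makes the assumption doubtful without disproving it.

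A reader might also infer a definite loss of power or a raised false-positive rate. A simulation with pain-driven dropout of about 22% on training and 7% on wait-list, analysed by ANCOVA at week 17, gives 68% power. With no true effect and both arms improving by 0.5 SD, it gives a spurious 0.09 SD and 7.4% type I error. The documents do not support these as properties of the plan. They state one 20% rate with no split by arm, and the stated analysis is a time-averaged difference. Part of the power loss is lost data that any method would suffer. With equal dropout of about 15% per arm and the same common trend, the spurious difference was −0.003 SD and rejection 5.0%. Wait-list participants may also leave, having no active treatment for 16 weeks, and retention measures cover both arms.

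Finally, both arms complete a weekly symptom battery. If it includes pain, which is not specified, the last pain value could be more recent than the last laboratory visit, and the bias for pain smaller. That would not settle which rule applies.

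**Conclusion.** The point holds. That the plan prescribes two incompatible treatments of the same withdrawals, with no order of priority, is certain from the text and needs no assumption. That carry-forward biases the estimate is conditional. It does so when the treatment effect is still building, even with random and equal dropout, or when symptoms drift and dropout differs between arms.

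The size under the stated assumptions is a shortfall of 0.08 SD at end of treatment (0.60 − 0.52) and about 0.04 SD time-averaged (0.40 − 0.36). These figures are illustrations. Other dropout patterns gave end-of-treatment values from 0.29 to 0.65 against 0.60, so carry-forward cannot be defended as reliably conservative, nor can a direction of bias be asserted. A wrong rule for the primary estimate should be corrected before analysis, and the case for doing so does not rest on any one simulated number.

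**What to change.** In Statistical Considerations:

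1. Delete the carry-forward rule.
2. Replace missing-completely-at-random with missing-at-random.
3. Name one primary method: the repeated-measures model already planned, fitted to all available baseline, week 6, 11 and 17 values of all randomised participants, or else multiple imputation by arm.
4. Add one delta-adjusted sensitivity analysis in which the outcomes of participants who drop out are made progressively worse, to cover symptom-related dropout.

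The plan includes all randomised participants and ignores noncompliance, so it is not shown to stop outcome collection when training stops. No change is asked for there.

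Cost: a few sentences of text and a little analysis time. No visits or measurements are added.
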